5.3 Treatment of subjects

The pivotal phase of the treatment period is 104 weeks. The extension phase is from 104 weeks to 208 weeks. The subjects will be randomised to one of the two groups (0.033 mg/kg/day group and 0.066 mg/kg/day group).

The trial includes two parallel treatment arms (0.033 mg/kg/day group and 0.066 mg/kg/day group). In the 0.033 mg/kg/day group and the 0.066 mg/kg/day group, the administration of trial products will be started subcutaneously in a daily regimen on the day of Visit 2.

The subjects in the 0.033 mg/kg/day group and in the 0.066 mg/kg/day group will be supplied NN-220 5 mg/1.5 mL pre-filled pen for 5mg and NN-220 10 mg/1.5 mL pre-filled pen for 5mg, respectively.

The dosage scale on pre-filled pen will be selected based on the subject's body weight at each visit. As a reference, listing for the dosage scale is shown in [Appendix C](#). The subjects in the 0.033 mg/kg/day group and in the 0.066 mg/kg/day group will be administered 0.033 mg/kg/day and 0.066 mg/kg/day, respectively, in the same dosage scale to keep the blindness.

NN-220 should be administered subcutaneously in the upper arm, thigh, abdominal wall or gluteal region in an orderly manner. The administration should not be repeated at the same injection site in a short period of time.

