6.2 Inclusion criteria

For an eligible subject, all inclusion criteria must be answered “yes” at Visit 1 (screening):

1. Informed consent obtained from each subject’s parent or the subject’s legally acceptable representative before any trial-related activities. Trial-related activities are any procedures that would not have been performed during normal management of the subject.
2. Japanese children with Noonan syndrome clinically diagnosed in one of the following ways
 - Clinically diagnosed by at least two medical experts using van der Burgt score list ([Table 6-1](#))
 - Clinically diagnosed by one medical expert using van der Burgt score list and diagnosed by result of genetic testing for Noonan syndrome.
 - Clinically diagnosed by one medical expert using van der Burgt score list and diagnosed by the same medical expert based on the results of centralised evaluation of facial change using van der Burgt score list.
3. Height SDS: -2 SDS or below (according to the Japanese reference data¹⁷)
4. Age: boys 3 to < 11 years, girls 3 to < 10 years
5. Height records must be available within the period between 40 and 64 weeks prior to Visit 1 (screening)
6. Prepubertal children (definition for girls breast and pubes of Tanner stage¹⁸ is I, and none of menses, and for boys testicular volume < 4 mL, and pubes and penis of Tanner stage is I)

Rationale for the inclusion criteria:

- Criterion 1 is applied through an ethical consideration, in accordance with the GCPs¹⁶.
- Criterion 2 is set in accordance with Noonan Syndrome: Clinical Features, Diagnosis, and Management Guidelines¹⁴ (hereinafter referred to as the “Guideline¹⁴”).

- Criterion 3; According to the consensus guidelines concerning the diagnosis and treatment of child- and adolescence-stage short stature due to GH hyposecretion, short stature is defined as height SDS for chronological age at -2 SDS or below. Since this trial is conducted with the aim of improving short stature, it is necessary to include only children with short stature.

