11.1 Randomisation

All subjects will be randomised to one of the two groups (0.033 mg/kg/day or 0.066 mg/kg/day) before procedures at Visit 2. The randomisation will be carried out in a 1:1 manner (0.033 mg/kg/day: 0.066 mg/kg/day) using the IV/WRS.

The trial sites should dispense trial products allocated by the IV/WRS in order to:

- secure available stock at site to cover the drug supply needed for the enrolled subjects
- ensure that no subjects are provided with trial products that will expire in between dispensing visits
- ensure that it will be possible to perform drug accountability of trial products by using the IV/WRS

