1.2 Scope of the statistical analysis plan

This Statistical Analysis Plan (SAP) is based on the statistical analyses of GHLIQUID-4020 as planned in the trial protocol.

Changes to the statistical methods proposed in this SAP and the reason for the change must be reported in the clinical trial report (CTR).

This SAP is based on the protocol version 2.0 (Dated 03 March 2016).

2 Statistical considerations

Analyses of all efficacy endpoints will be performed based on the full analysis set (FAS). The primary analysis of the primary endpoint will be repeated on the per protocol (PP) analysis set.

Safety endpoints will be summarised using the safety analysis set (SAS).

The impact of protocol deviations and outliers may be investigated further in sensitivity analyses if deemed relevant.

Missing values for endpoints other than OGTT, HbA_{1c} and bone age will be imputed using the last observation carried forward (LOCF) method.

All endpoints will be summarised descriptively at each visit by treatment using observed data. After 104 weeks of treatment, descriptive statistics will be presented based on both observed and LOCF imputed data. Endpoints that are analysed untransformed and endpoints that are not formally analysed are summarised by the arithmetic mean, standard deviation (SD), median, and minimum and maximum value. Endpoints that are analysed log-transformed are summarised by the geometric mean, coefficient of variation (CV), median, minimum and maximum value.

LOCF imputed data will be used as the basis for plotting data.

A formal statistical test will only be performed at 104 weeks. Presentation of results from a statistical analysis will include the estimated mean treatment effects (LSMeans). Estimated mean

treatment differences (or ratios) will be presented together with two-sided 95% confidence intervals and p values for all endpoints analysed statistically.

For endpoints measured over time mean values will be plotted to explore the trajectory over time. Data collected before randomisation will only be summarised descriptively.

Statistical analysis will be performed twice, at 104 weeks and at the end of trial including extension phase.

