2.3 Primary endpoint

The primary endpoint is change in height SDS from baseline to 104 weeks of treatment according to the Japanese reference dataⁱⁱ. A height SDS will be also calculated according to the Noonan syndrome reference data in Japaneseⁱⁱⁱ.

Statistical analysis

Since the primary objective of this trial is to evaluate the growth promoting effect of NN-220, the following hypothesis will be statistically tested; $H_0: \mu_1 = \mu_2$ vs. $H_1: \mu_1 \neq \mu_2$, where μ_i is the population mean, $i = 1, 2$ represents 0.033 mg/kg/day and 0.066 mg/kg/day, respectively. Primary analysis for the primary endpoint will be performed based on the ANCOVA model with treatment as a fixed effect and baseline height SDS as a covariate.

Sensitivity analysis

The same analysis as for the primary endpoint will be repeated on the PP analysis set.

All height SDS measurements at scheduled time points after randomisation will be analysed in a linear mixed model with treatment, time and interaction between treatment and time as fixed effects, baseline height SDS and interaction between baseline and time as a covariate and subject as a random effect. This approach assumes that data are missing at random according to the taxonomy defined by Rubin (1976)^{iv}. Treatment differences at 104 weeks will be estimated using this model.

Any marked difference concerning treatment differences between the sensitivity results and the result from the primary endpoint will be commented upon in the CTR.

Exploratory analysis

In order to investigate effects of sex, age at start of treatment and baseline height SDS on the primary endpoint, change in height SDS from baseline to 104 weeks of treatment will be analysed based on the ANCOVA model with treatment and sex as fixed effects and age at start of treatment and baseline height SDS as covariates. Parameter estimates for sex, age at start of treatment and baseline height SDS will be presented together with two-sided 95% CIs and p values.

Height SDS (Noonan syndrome reference data in Japanese)

In addition to height SDS according to the Japanese reference data, height SDS will be also calculated according to the Noonan syndrome reference data in Japanese. The change in height SDS (Noonan syndrome reference data in Japanese) from baseline to 104 weeks of treatment will be

analysed based on the ANCOVA model with treatment as a fixed effect and baseline height SDS (Noonan syndrome reference data in Japanese) as a covariate.

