Change in bone age and bone age/chronological age from baseline to 104 weeks of treatment will be analysed based on ANCOVA model with treatment as a fixed effect and baseline as a covariate. A 95% confidence interval of the treatment difference will be provided. Yearly Δ bone age/ Δ chronological age will be summarised and graphically presented.

Vital signs (blood pressures and pulse)

The measurements and their change from baseline during 104 weeks of treatment will be summarised descriptively.

Urinalysis

The measurements and their change from baseline during 104 weeks of treatment will be summarised descriptively.

Blood coagulation

The measurements and their change from baseline during 104 weeks of treatment will be summarised descriptively.

ECCG

The measurements and their change from baseline during 104 weeks of treatment will be summarised descriptively.

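### The bone age/chronological age ANCOVA leaves out entry age, which drives that ratio by construction, so its dose difference carries avoidable age-related noise and chance age imbalance

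*SAP*

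**What the plan says.** The bone age part of SAP 2.4.2 covers three measures. Two are tested: "Change in bone age and bone age/chronological age from baseline to 104 weeks of treatment will be analysed based on ANCOVA model". The model is an "ANCOVA model with treatment as a fixed effect and baseline as a covariate", and a 95% confidence interval is given for the treatment difference. The third measure, yearly change in bone age over change in chronological age, is descriptive only: "chronological age will be summarised and graphically presented". Protocol 17.4.2 specifies the same analyses.

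Entry ages are wide (Protocol 6.2): "Age: boys 3 to < 11 years, girls 3 to < 10 years". Allocation is simple in description (Protocol 11.1): "The randomisation will be carried out in a 1:1 manner", with no stratification by age mentioned. The SAP uses age as a covariate in one place, the exploratory model for height SDS in SAP 2.3, which takes "age at start of treatment and baseline height SDS as covariates". Under SAP section 2, bone age is exempt from carrying the last value forward: "Missing values for endpoints other than OGTT, HbA_{1c} and bone age will be imputed".

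**The concern.** Change in bone age/chronological age is the one tested endpoint whose outcome is divided by the child's age. Age therefore scales the outcome directly, whether or not it predicts response to treatment. A model with only the baseline ratio puts the age-driven part of the outcome into the residual, and any chance difference in mean age between two arms of about 21 to 24 children into the estimated dose difference.

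At stake is how clearly the trial can show whether the higher dose advances bone age relative to chronological age, which bears on how a gain in height at that dose is read.

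**Working it through.** **Plan figures.** The documents state no effect size, SD or power for bone age. Table 17-1 concerns the primary endpoint. Its 21 per group (difference 0.45, SD 0.5, two-sided 5% t-test) reproduces: exact power is 0.812 at 21 and 0.792 at 20. Protocol 6.1 expects 42 completers, so 21 per arm is used below.

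**Identity (no assumptions beyond a two-year interval).** Protocol 5.3: "The pivotal phase of the treatment period is 104 weeks", that is 1.99 years, taken as 2. With baseline bone age ra:

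change in ratio = (ra + d)/(a + 2) - r = (d - 2r)/(a + 2).

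One extra bone-age year adds 1/(a + 2):
- age 3: 1/5 = 0.200
- age 10, the girls' limit: 1/12 = 0.083, so 12/5 = 2.4-fold
- just under 11, the boys' limit: about 1/13 = 0.077, so 13/5 = 2.6-fold

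Example with r = 0.8 and d = 2.5: (2.5 - 1.6)/5 = 0.180 at age 3 and 0.9/13 = 0.069 at age 11. If d = 2r, the change is zero at every age. This is why the value of an age term depends on how far the mean advance departs from twice the baseline ratio.

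**Simulation (all bone-age inputs assumed).** 42 children, ages uniform over the entry range, baseline ratio mean 0.7 to 1.0 (SD 0.12), mean two-year advance 2.0 to 3.0 years, SD of advance 0.4 or 0.7, dose effect 0.3 bone-age years; 24 settings, 1,500 trials each. Selected settings:

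| Baseline ratio | Advance | SD | SE, planned | SE, with age | SE reduction | Power, planned / with age | Power, bone age in years |
|---|---|---|---|---|---|---|---|
| 1.0 | 2.0 | 0.4 | 0.0159 | 0.0162 | none | 0.62 / 0.61 | 0.66 |
| 1.0 | 2.0 | 0.7 | 0.0270 | 0.0271 | none | 0.26 / 0.25 | 0.27 |
| 0.8 | 2.0 | 0.4 | 0.0171 | 0.0166 | 3% | 0.54 / 0.58 | 0.66 |
| 0.8 | 2.5 | 0.7 | 0.0299 | 0.0280 | 6% | 0.24 / 0.25 | 0.28 |
| 0.8 | 2.5 | 0.4 | 0.0192 | 0.0164 | 15% | 0.45 / 0.58 | 0.63 |
| 0.7 | 3.0 | 0.7 | 0.0328 | 0.0290 | 12% | 0.20 / 0.26 | 0.29 |
| 0.7 | 3.0 | 0.4 | 0.0244 | 0.0164 | 33% | 0.32 / 0.56 | 0.65 |

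The reduction is 1 minus (SE with age / SE planned). It is under 12% in 18 of the 24 settings, four of which show none. In the other six it is 14.5% to 32.5%; all six have SD 0.4 and a mean advance of at least 2.5 years. A separate set of simulations at 21 per arm gave about 0 to 13%, with at most about 2 points of power lost where age carried no information.

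**Chance imbalance.** The arms' mean ages differ by chance with SD about 0.67 years. Each year of imbalance shifts the planned estimate by 0.002 to 0.027 ratio units, so a one-SD imbalance moves it by 0.67 × 0.002 = 0.001 to 0.67 × 0.027 = 0.018, against a mean effect of about 0.037. With age in the model the shift per year is within 0.002 of zero.

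**Bias.** With no dose effect (one setting, 4,000 trials), the planned model rejects in 4.9% of trials and the mean estimate is 0.000.

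**Age mix.** The mean of 0.3/(a + 2) is 0.047 for entry ages 3 to 6, 0.036 for 3 to 11 and 0.028 for 7 to 11. The average estimate is about 0.037 with or without the age term, so the covariate leaves this dependence in place.

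**The case against.** The strongest reply is that the sensitive test is already planned. The sentence that specifies the ratio analysis also specifies an ANCOVA of change in bone age in years. That outcome has no age divisor, and it had more power than the ratio ANCOVA in all 24 settings. The ratio is one part of one of ten secondary safety endpoints, with no stated hypothesis or power, and its model follows the treatment-plus-baseline form used throughout the SAP. The gain from an age term can be zero, and the documents hold no bone-age data to settle which setting applies. All of this stands. It makes the point small but does not remove it, since the ratio will still be reported with a confidence interval and p value.

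Three stronger readings are tempting, and the documents do not support them.

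- *The dose comparison is biased.* Allocation is randomised, and the simulated error rate and mean under no effect are as they should be. Only precision and chance imbalance are at issue.
- *Adding age cures the 2.6-fold scaling.* That scaling is a treatment-by-age feature of the ratio, and a main effect of age does not touch it.
- *The yearly ratio of bone-age change to age change should be tested instead, for a large gain in power.* For completers the elapsed time is 104 weeks within 14 days, so this measure over two years is close to change in bone age divided by 2. In simulation the two correlate at 0.998 to 0.999 and their powers differ by no more than 0.01. Testing it would repeat a planned analysis. Extending it to X-rays taken at withdrawal would mix intervals of different length: dividing by 0.5 rather than 2 years multiplies bone-age measurement error fourfold. It would also change the stated week-104 endpoint, for few children at the planned 10% withdrawal.

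**Conclusion.** The point holds as a minor matter of precision. Entry age determines the scale of the ratio outcome, it is collected, the SAP uses it elsewhere, and it is missing from this model. The 2.6-fold figure is exact but is an upper limit, reached only for a boy just under 11 compared with a child of 3; against age 10 it is 2.4. The benefit of adding age runs from nothing to roughly a 13% lower standard error in most settings, and up to about a third when the advance is large and its SD small. These sizes rest on assumed ratios, advances, SDs and uniform entry ages. The identity and the absence of age from the model do not. The size of the ratio's dose effect will depend on the age mix whichever model is used, which is a reason to rest the bone-age conclusion on the analysis in years.

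**What to change.** In SAP 2.4.2, add age at start of treatment as a covariate in the ANCOVA of change in bone age/chronological age, and list it in SAP section 3 with the other changes from the protocol. State that the planned ANCOVA of change in bone age in years is the main dose comparison for bone age and that the ratio is supportive. Note beside the ratio result that its size depends on the ages enrolled. Carry the same model into any week-208 analysis under SAP 2.4.3. The yearly ratio can stay descriptive.

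The cost is one degree of freedom and up to about 2 points of power if age proves uninformative. No new data, visit or procedure is needed.

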2.4.3 Endpoints for the whole trial including the extension phase

The period of the extension phase is 104 weeks, and the period of the whole trial will be 208 weeks [104 weeks in the pivotal phase and 104 weeks in the extension phase]. However, if the indication has not yet been approved or rejected by the PMDA at 208 weeks for the first subject, the period for the extension phase will be extended for at least 26 weeks (6 months).

The endpoints at 208 weeks for the whole trial including the extension phase are defined in the same way as for the pivotal phase.

All efficacy and safety endpoints and parameters will be summarised and analysed in the same way as for the 104 weeks.

TEAEs will be defined as an event that has onset date on or after the first day of exposure to NN-220 and no later than 7 days after the last day of NN-220 treatment.

3 Changes to the statistical analyses planned in the protocol

The following changes from the protocol are implemented in this SAP

Terminology

“Efficacy parameters” is changed to “secondary efficacy endpoints” in section 4.2 in the protocol version 2 but it is not reflected to the section 17. In this SAP, it is changed to “secondary efficacy endpoints” from “efficacy parameters”.

Exploratory analysis on the primary endpoint

In order to investigate effects of sex, age at start of treatment and baseline height SDS on the primary endpoint, change in height SDS from baseline to 104 weeks of treatment is analysed based on the ANCOVA model with treatment and sex as fixed effects and age at start of treatment and baseline height SDS as covariates.

Statistical analysis of height SDS according to the Noonan reference

A statistical analysis on change from height SDS according to the Noonan reference in the protocol is included.

Derivation of AUC

Imputation of missing data for each individual profile is specified.

Definition of treatment emergent adverse event

The date of visit 2 (0 week) instead of the first day of exposure to NN-220 is used for a definition of a treatment emergent adverse event since the first day of exposure to NN-220 is not available in the database by the end of treatment.

Treatment emergent adverse event based on pre-defined MedDRA search

Summary tables based on system organ class and preferred term are made for treatment emergent adverse event based on pre-defined MedDRA search.

4 References

-

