12.3 Follow-up of adverse events

All SAEs must be followed up until the outcome of the event is “recovered”, “recovered with sequelae” or “fatal”, and until all queries have been resolved. Cases of chronic conditions, cancer or AEs ongoing at time of death (where death is due to another AE) may be closed with the outcome “recovering” or “not recovered”, when the subject has completed the follow up period.

The follow-up information should only include new (corrections or new or additional) information and should be reported **within 24 hours** of obtaining knowledge of the information. This is also the case for previously non-serious AEs which subsequently become SAEs.

Follow-up information on MESIs (not also fulfilling the SAE criteria) should only include new (corrections or new or additional) information and should be reported **within 14 calendar days** of obtaining knowledge of the information. This is also the case for previously non-serious AEs which subsequently fulfil the MESI criteria.

Non-serious AEs (not also fulfilling the MESI criteria) must be followed until the outcome of the event is “recovering”, “recovered” or “recovered with sequelae” or until the end of the follow-up period stated in the protocol, whichever comes first, and until all queries related to these AEs have been resolved. Cases of chronic conditions or cancer or AEs ongoing at time of death (where death is due to another AE) may be closed with the outcome “recovering” or “not recovered”.

Queries or follow-up requests from Novo Nordisk should be responded to within 14 calendar days.

The investigator must forward follow-up information on SAEs to Novo Nordisk within 24 hours of obtaining the follow-up information by using a new AE form and/or a safety information form marked as follow-up.

The investigator must forward follow-up information on MESIs (not fulfilling the SAE criteria) to Novo Nordisk within 14 calendar days of obtaining the follow-up information by using a new AE form and/or a safety information form and/or MESI form marked as follow-up.

The investigator must forward follow-up information on non-serious AEs (not fulfilling the MESI criteria) as corrections to the original AE form, or by using a new AE form marked as follow-up.

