17.4.3 Endpoints for the whole trial including the extension phase

The period of the extension phase is 104 weeks, and the period of the whole trial will be 208 weeks [104 weeks in the pivotal phase and 104 weeks in the extension phase]. However, if the indication has not yet been approved or rejected by the PMDA at 208 weeks for the first subject, the period for the extension phase will be extended for at least 26 weeks (6 months).

The endpoints at 208 weeks for the whole trial including the extension phase are defined in the same way as for the pivotal phase.

Protocol
Trial ID: GHLIQUID-4020
UTN: U1111-1131-5892

~~CONFIDENTIAL~~

Date: 21 March 2013
Version: 1.0
Status: Final
Page: 72 of 87

Novo Nordisk

All efficacy and safety endpoints and parameters will be summarised and analysed in the same way as for the 104 weeks.

TEAEs will be defined as an event that has onset date on or after the first day of exposure to NN-220 and no later than 7 days after the last day of NN-220 treatment.

18 Ethics

The trial will be conducted in compliance with ICH GCP²⁵, applicable regulatory requirements, and in accordance with the Declaration of Helsinki¹⁵.

At the termination of the trial, the subject and investigator will decide on the best available treatment.

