^{a)} The extension phase can be further extended for 26 weeks for subjects who will complete visit 20 no later than the end of the month following marketing approval date for use of Norditropin for treatment of 'short stature due to Noonan syndrome' who consent to receive the trial products during the period. For subjects who will receive trial treatment for further 26 weeks, visits 21 and 22 should be conducted.

^{b)} For subjects who will complete the trial treatment at week 208, the assessment will not be performed at visit 20. For subjects who will receive trial treatment for further 26 weeks, the assessment should be performed at visit 20.

^{c)} For subjects who will complete the trial treatment at week 208, the end of trial form should be completed at visit 20. For subjects who will receive trial treatment for further 26 weeks, the end of trial form should be completed at visit 22.

2.25 Protocol, Section 12.2 Reporting of adverse events, page 55

All events meeting the definition of an AE must be collected and reported. This includes events from the first trial-related activity after the subject's parent or the subject's legally acceptable representative has signed the informed consent until the completion of procedures at Visit 20 or Visit 22 (if applicable). The events must be recorded in the applicable forms in a timely manner.

2.26 Protocol, Section 17.4.3 Endpoints for the whole trial including the extension phase, page 70

The period of the extension phase is 104 weeks, and the period of the whole trial will be 208 weeks [104 weeks in the pivotal phase and 104 weeks in the extension phase]. However, ~~if the indication has not yet been approved or rejected by the PMDA at 208 weeks for the first subject, the period for the extension phase will be extended for at least 26 weeks (6 months)~~ the extension phase can be further extended for 26 weeks (to week 234) for subjects who will complete visit 20 (week 208) no

later than the end of the month following marketing approval date for use of Norditropin for treatment of ‘short stature due to Noonan syndrome’ who consent to receive the trial products during the period.

The endpoints at 208 weeks for the whole trial including the extension phase are defined in the same way as for the pivotal phase. *Data collected in the further extended extension phase will only be summarised descriptively.*

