All efficacy and safety endpoints and parameters *after 208 weeks of treatment* will be summarised and analysed in the same way as for the 104 weeks.

2.27 SIIC, Section 1.2 What is a clinical?, page 4

This trial will be classified as post marketing clinical trial after getting marketing approval for treatment of ‘short stature due to Noonan syndrome’ in Japan, and then the term “clinical trial” will be replaced with “post marketing clinical trial”. Other implementation is not changed.

2.28 SIIC, Section 1.5 Treatment in this trial, page 4

You will be provided with NN-220 on Visit 2, and please subcutaneously inject it once a day from that day until the previous night of Visit 20 *or* Visit 22.

2.29 SIIC, Section 1.6 Trial period, page 5

The trial period of this trial is 208 weeks. However, ~~if the indication has not been approved by PMDA at 208 weeks for the first subject, the period for the extension phase will be extended. You will be explained before 208 weeks for the first subject whether the period for the extension phase will be extended or not~~ *if the 208 week-treatment is completed by the end of next month of marketing approval date, 26 weeks can be extended for the treatment period (Visit 21 and Visit 22 are added in case of extending the period).* In case NN-220 is not approved as a “Medicine”, specifically, when this developmental program is terminated or if the MHLW rejects the marketing application, this trial will be stopped and the treatment for your child with NN-220 will be ended.

Please continue the treatment until the previous night of Visit 20 *or* Visit 22. At Visit 20 *or* Visit 22, the trial will be completed.

If your child participates in this trial, the number of visiting the hospital/clinic is 20 *or* 22. If your trial doctor needs your child to visit the hospital/clinic at short intervals, more visits may be requested.

2.30 SIIC, Section 1.7.2 Trial schedule, page 6

[figure not shown]

Figure 1-1 Trial diagram (updated figure is presented)

2.31 SIIC, Section 1.7.2 Trial schedule, page 8

Table 1-1 Trial schedule

Item \ Period (weeks)	Visit 13	Visit 14	Visit 15	Visit 16	Visit 17	Visit 18	Visit 19	Visit 20	Visit 21 ^{*2}	Visit 22 ^{*2}
	Time (weeks) from Visit 2									
	117	130	143	156	169	182	195	208	221	234
Need to be fasting				○				○		○
Medical examination/interview ^{*1} , measurement of height, body weight, blood pressure, and pulse	○	○	○	○	○	○	○	○	○	○
Electrocardiogram (ECG)		○		○		○		○		○

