2.4.2 Safety endpoints

Secondary safety endpoints during 104 weeks are as follows:

- Incidence of treatment emergent AEs during 104 weeks of treatment
- Change in IGF-I from baseline during 104 weeks of treatment
- Change in HbA_{1c} from baseline to 104 weeks of treatment
- Change in clinical laboratory tests from baseline during 104 weeks of treatment
- Change in glucose tolerance (AUC of glucose and AUC of insulin) based on the OGTT from baseline to 104 weeks of treatment
- Change in bone age and bone age/chronological age from baseline to 104 weeks of treatment, and (yearly [change in bone age] / [change in chronological age]) (yearly [Δ bone age/ Δ chronological age])
- Change in vital signs (blood pressures and pulse) from baseline during 104 weeks of treatment
- Change in urinalysis from baseline during 104 weeks of treatment
- Change in blood coagulation test from baseline during 104 weeks of treatment
- Change in ECG from baseline during 104 weeks of treatment

Incidence of treatment emergent adverse events during 104 weeks of treatment

AEs will be coded using the current version of the Medical Dictionary for Regulatory Activities (MedDRA). All AEs will be presented based on system organ class and preferred terms.

A treatment emergent adverse event (TEAE) is defined as an event that has onset date on or after the date of visit 2 (0 week) and no later than the date of Visit 12 (104 weeks). For withdrawal

subjects, AEs with onset date no later than 7 days after the last day of NN-220 treatment will be included in the TEAE.

TEAEs are summarised descriptively, whereas non-treatment emergent AEs are presented in listings. TEAE data will be displayed in terms of the number of subjects with at least one event (N), the percentage of subjects with at least one event (%), the number of events (E) and the event rate per 100 years (R). Furthermore, TEAE data are summarised by seriousness, severity, relation to treatment, relation to device, withdrawal due to AEs and outcome.

Furthermore summary tables based on system organ class and preferred term are made for

- All TEAEs
- Serious TEAEs
- Possibly or probably related TEAEs
- Severe TEAEs
- Cardiac disease TEAEs
- TEAEs with preferred term that are experienced by at least 5% of the subjects in any treatment arm or by at least 5% of all subjects
- Medication errors
 - HLGTS: Medication errors, Device issues and Product Quality Issue

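### The whole-trial TEAE window has no Visit 20 cut-off, so read literally the week-208 incidence includes about 26 extra weeks for children who continue to week 234

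*SAP*

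**What the plan says.** SAP 2.4.3 states that "the period of the whole trial will be 208 weeks" and that the 208-week endpoints are defined as they were for the pivotal phase. Protocol 17.4.3 says the same.

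For the pivotal phase, SAP 2.4.2 ends the TEAE window "no later than the date of Visit 12 (104 weeks" weeks being the nominal time of that visit). Only withdrawn children get the allowance of 7 days after last dose. Protocol 17.4.2 closes the window in the same way.

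For the whole trial, SAP 2.4.3 counts events from first "exposure to NN-220 and no later than 7 days after the last day of NN-220 treatment". Protocol 17.4.3 also ends the window "no later than 7 days after the last day of NN-220 treatment". This applies to every child, and neither text names Visit 20 or week 208 as a limit.

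The protocol amendment of 29 March 2017 lets children who complete Visit 20 by the end of the month after marketing approval, and who consent, continue for 26 weeks to week 234, with Visits 21 and 22. Its item 2.26 adds to Protocol 17.4.3 that "Data collected in the further extended extension phase will only be summarised descriptively". It also attaches the words about 208 weeks of treatment to the sentence on endpoint analyses. It does not alter the TEAE definition. The SAP is based on protocol version 2.0 of 3 March 2016, so it predates this amendment. Its own older text already allowed an extension of at least 26 weeks.

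**The concern.** For a child who stops at Visit 20, last dose plus 7 days falls close to week 208. For a child who continues, the same rule closes the window just after week 234. Events in weeks 208 to 234 therefore qualify as whole-trial TEAEs in one group of children and cannot occur on treatment in the other.

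The sentence making post-208 data descriptive does not separate them, because TEAEs are always summarised descriptively (SAP 2.4.2) and no separate table or cut-off date is named.

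TEAE incidence is the first-listed secondary safety endpoint. The planned display is N, %, number of events and rate per 100 years. The first three are not adjusted for exposure. The rate is protected only if exposure is cut at the same date as the events, which the SAP does not specify. At stake is whether a figure presented as the 208-week incidence describes 208 weeks.

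**Working it through.** **Inputs**
- Whole-trial endpoint: 208 weeks (SAP 2.4.3). Further extension: to week 234 (amendment, section 1.1).
- Visit windows: ±14 days at Visits 20 and 22 (amended flow chart).
- Illustrative event rate: 119 events in 179 treatment-years in the Swedish trials (Protocol 3.1.1). Carrying this over is an assumption.
- Expected completers: 42 (Protocol 6.1).
- Planned first visits: 30 August 2013 to 26 December 2014 (Protocol 7). Planned last patient last visit: December 2018 (first amendment, item 2.2).

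**1. Reproduce the plan's extension length.** 234 − 208 = 26 weeks = 182 days, as stated. 26/208 = 12.5% more follow-up. With the visit windows, Visit 20 to Visit 22 can span 22 to 30 weeks, so 26 is nominal.

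**2. Events per continuing child.** 119/179 = 0.665 per year. 0.665 × 182/365.25 = 0.33.

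**3. Base over 208 weeks.** 208 weeks = 1,456 days. 0.665 × 1,456/365.25 = 2.65 per child; × 42 = about 111 events.

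**4. How many could continue.** The documents give no number, so this is a ceiling from the planned dates.
- 234 weeks = 1,638 days. Counting back from 31 December 2018, treatment must start by about 7 July 2014.
- 30 August 2013 to 7 July 2014 is 311 days. The planned recruitment period is 483 days.
- With even accrual, 311/483 = 64%; × 42 = about 27 children.
- This puts treatment start on the day of the first visit. With the full 4 weeks of screening it is 283/483 = 59%, or about 25 children.
- The lower limit is 0, because continuation also needs a late enough approval date and consent.

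**5. Extra events in the week-208 count.**

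| Children continuing (of 42) | Extra events | Share of 111 |
|---|---|---|
| 0 | 0 | 0% |
| 10 | 3.3 | 3.0% |
| 21 | 7.0 | 6.3% |
| 27 | 27 × 0.331 = 8.9 | 8.0% |

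**6. After the fix.** With the window closed at the Visit 20 date, the excess for continuing children falls from 182 days to 0.

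**The case against.** The strongest reply is that the amendment already draws a line at week 208. Amended Protocol 17.4.3 ties the endpoint analyses to 208 weeks of treatment and places later data in a category of their own. This shows the intent. It does not override an explicit TEAE rule that ends at last dose, and a programmer following that rule would include the later events.

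The two windows also differ for an understandable reason. At the 104-week lock most children are still on treatment and have no last dose, so a visit date is needed; at the end of the trial everyone has one. That explains the rule, and makes it suitable for an all-treatment table. It does not make it suitable for a 208-week endpoint once some children are treated beyond week 208. The outdated extension wording in the SAP is a matter of version timing and is not itself an error.

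Three stronger readings are tempting but not supported:

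- **All 42 completers might continue, giving about 14 extra events (42 × 0.331 = 13.9).** The planned December 2018 last visit rules this out unless that date slips. None of the changes printed in the 29 March 2017 amendment revises the trial schedule in Protocol 7.
- **The extra follow-up might be unbalanced between doses.** Enrolment and approval dates are unrelated to randomised dose, and investigators and subjects stay blinded until the second database lock (Protocol 11.2). Rough balance is expected.
- **The window might be thought defective because it outlasts adverse-event collection.** Collection runs "until the completion of procedures at Visit 20 or Visit 22 (if applicable", and families are told "Please continue the treatment until the previous night of Visit 20", so a completer's window closes 7 − 1 = 6 days after the last scheduled contact. At the Swedish rate this is 0.665 × 6/365.25 = 0.011 events per child, or under 0.5 in 42 children. It adds no false events and does not merit separate correction.

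**Conclusion.** The point holds as a missing cut-off in the definition of a 208-week safety endpoint. Read literally, the week-208 N, % and event count include about 26 extra weeks (12.5%) for continuing children only. The illustrative size is 0.33 events per continuing child and at most roughly 9 events on about 111.

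Those event figures rest on the Swedish rate carrying over, a constant rate over time, 42 completers, even accrual and the planned December 2018 last visit. The structural finding rests on none of them, provided at least one child continues. The effect is on the 208-week incidence figures. It gives no material reason to doubt the comparison between doses.

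**What to change.** Before the second database lock, amend SAP 2.4.3 and Protocol 17.4.3 as follows:

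- For the week-208 analysis, end both the TEAE window and the exposure denominator at the Visit 20 date. For children withdrawn earlier, keep last dose plus 7 days. This mirrors the Visit 12 rule.
- Tabulate events from Visit 20 to Visit 22 separately by dose, with their own exposure.
- If wanted, keep an all-treatment table to last dose plus 7 days, labelled as such.

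The cost is a wording change and one extra table. A few events move out of the 208-week table into the separate one, and none is lost. No new trial procedure is needed.
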